3.1.2. Treatment Period

The treatment period will begin on Cycle 1 Day 1. Cycle 1 will be 28 days; all subsequent cycles will be 21 days. Patients will be treated until unacceptable toxicity, death, progressive disease, treatment discontinuation at the discretion of the Investigator, or withdrawal of consent (maximum treatment duration with pembrolizumab is 24 months).

Patients with first evidence of progressive disease and no clinical deterioration may continue study treatment until a repeat scan within 4 to 6 weeks confirms disease progression.

To account for atypical disease response to immune therapy, Investigators are encouraged to follow immune-modified Response Evaluation Criteria in Solid Tumors (iRECIST) criteria (criteria based on RECIST v 1.1 for response and progressive disease, but adapted to account for the tumor response seen with immunotherapeutic drugs as described in Appendix 3) for treatment decision making, including confirmation of unconfirmed progressive disease with additional imaging.

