9.6.2. Secondary Efficacy Endpoints Analysis

Secondary efficacy endpoints will include DOR, disease control rate (DCR), PFS, and OS:

- **Duration of response** (DOR): defined as the interval from date of first observed CR or PR to the date of documented disease progression or death due to any cause, whichever occurs first. All patients who have not progressed will be censored at the last non-missing tumor assessment. Estimates of median DOR with 95% CI will be determined by dosing regimen using Kaplan-Meier methods.
- **Disease control rate** (DCR): defined as the percentage of patients having a CR, PR, or stable disease at any time during treatment, as assessed by the Investigator using RECIST v1.1. DCR will be summarized by dosing regimen with 95% CI obtained by Clopper-Pearson Exact methods.
- Progression-free survival (PFS): defined as the interval from the start of study drug treatment to the date of first documented disease progression or death from any cause, whichever occurs first. Responding patients and patients who are lost to follow-up will be censored at their last tumor assessment date. Estimates of median PFS with 95% CI will be determined by dosing regimen using Kaplan-Meier methods. The 95% CI around the PFS and OS rates at 12 months (56 weeks) will also be presented.
- Overall survival (OS): defined as the interval from the start of study drug treatment to date of death for any reason. Surviving patients and patients who are lost to follow-up will be censored at their contact date. Estimates of median OS with 95% CI will be determined by dosing regimen using Kaplan-Meier methods.

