CR: Disappearance of all non-target lesions and normalization of tumor marker levels. All lymph nodes must be non-pathological in size (< 10 mm in the short axis).

Non-CR/non-PD: Persistence of 1 or more non-target lesions or tumor marker levels maintained above normal limits.

PD: Unequivocal progression of existing non-target lesions or the appearance of 1 or more new lesions.

Overall Response

The following table shows the criteria for the assessment of overall response at each time point for subjects who have measurable lesions at baseline.

Evaluation of Overall Response at Each Time Point

Target Lesions	Non-Target Lesions	New Lesions	Overall Response
CR	CR	No	CR
CR	Non-CR/non-PD	No	PR
CR	Not evaluated	No	PR
PR	Non-PD/not evaluated	No	PR
SD	Non-PD/not evaluated	No	SD
NE	Non-PD	No	NE
PD	Any	Yes or no	PD
Any	PD	Yes or no	PD
Any	Any	Yes	PD

Source: RECIST version 1.1 criteria.

Abbreviations: CR = complete response; NE = not evaluable; PD = progressive disease; PR = partial response; RECIST = Response Evaluation Criteria in Solid Tumors; SD = stable disease.

Best Overall Response

Best overall response (BOR) in this study is defined as the BOR across all time points, eg, a subject who has SD at first assessment, partial response at second assessment, and PD at last assessment has a best overall assessment of PR. If SD is assessed as the BOR, it must also meet the SD criteria at least once after study entry at 6 weeks or longer from baseline. If SD is the best time point response and the minimum time requirement is not met, the subject's best response will depend on subsequent assessments eg, a subject who has SD at first assessment and PD at second assessment and does not meet the minimum duration for SD, will have a best overall assessment of PD. The same subject lost to follow-up after the first SD assessment would be considered unevaluable.

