3.4 Efficacy and Safety Variables

3.4.1 *Efficacy Variables*

3.4.1.1 *Primary Efficacy Variable*

Tumor responses will be assessed by the Investigator per RECIST v1.1 using MRI or CT scan assessments. For patients receiving pembrolizumab, tumor responses will also be assessed per immunologic RECIST (iRECIST). Tumor imaging will be repeated to confirm disease progression using iRECIST.

The primary efficacy endpoint is ORR, defined as the percentage of patients with a CR or PR as assessed by RECIST v1.1 within the first 26 weeks (6 months) of treatment. The ORR will also be calculated using iRECIST for patients receiving pembrolizumab.

3.4.1.2 *Secondary Efficacy Variables*

Secondary efficacy endpoints include the following:

- Time to response (TTR) – defined as the interval from the start of study drug treatment to the date of first documented CR or PR per RECIST or iRECIST.
- Duration of response (DOR) – defined as the interval of time from the date of first observed CR or PR to the date of documented disease progression or death due to any cause, whichever occurs first. Dates of progression and censoring will be determined as described in [Section 4.5.5.2](#);
- Disease control rate (DCR) – defined as the percentage of patients having a CR, PR, or stable disease (SD) at any time during treatment;
- Progression-free survival (PFS) – defined as the interval of time from the start of study drug treatment to the date of first documented disease progression, initiation of new antineoplastic therapy, withdrawal of consent, loss to follow-up, or death due to any cause, whichever occurs first. Dates of progression and censoring will be determined as described in [Section 4.5.5.2](#); and
- Overall survival (OS) – defined as the interval of time from the start of study drug treatment to the date of death due to any cause. Patients without

documentation of death at the time of analysis will be censored at the date the patient was last known to be alive.

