4.5.5.2 Handling of Dropouts or Missing Data

Objective response rate and disease control rate are based on those patients with available data (baseline and post-baseline response assessment). Non-evaluable patients are considered non-responders and will be included in the denominator. The analysis of PFS and DOR will be right-censored according to the conventions described in [Table 2](#). These conventions are based on the FDA Guidance for Industry *Clinical Trial Endpoints for the Approval of Cancer Drugs and Biologics* ([2018](#)) and *Clinical*

Trial Endpoints for the Approval of Non-Small Cell Lung Cancer Drugs and Biologics (2015).

Table 2 Conventions for Censoring for DOR and PFS

Situation	Date of Progression or Censoring	Outcome
No baseline tumor assessments	Randomization (if applicable), or enrollment	Censored
New anti-cancer treatment started before documentation of PD or death	Date of last disease assessment without documentation of PD before start of new treatment	Censored
Death or progressive disease (PD) immediately after more than one consecutively missed disease assessment visit	Date of last disease assessment visit without documentation of PD that is before the first missed visit	Censored
Alive and without PD documentation	Date of last disease assessment	Censored
Treatment discontinuation for undocumented progression, toxicity, or other reason	Date of last disease assessment without documentation of PD	Censored
Death or PD between planned disease assessments	Date of death or first disease assessment showing PD, whichever occurs first	Not Censored
Death or PD after more than one missed visit	Date of last disease assessment without documentation of PD	Censored

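### Best response, ORR and DCR have no cut-off at first RECIST progression, so a patient with a PFS event can also count as disease-controlled or as a responder

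*Protocol*

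**What the plan says.** **Response endpoints.** Protocol Appendix 3 (Best Overall Response) reads: "Best overall response (BOR) in this study is defined as the BOR across all time points". DCR is "defined as the percentage of patients having a CR, PR, or stable disease at any time during treatment" in Protocol 9.6.2, and SAP 3.4.1.2 words it the same way. SAP 3.4.1.1 counts for ORR a "CR or PR as assessed by RECIST v1.1 within the first 26 weeks (6 months) of treatment". That is a calendar limit, not a progression limit. SAP 4.5.5.2 confines its censoring table to PFS and DOR. For ORR and DCR it deals only with available data and non-evaluable patients.

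**Progression endpoints.** Protocol 9.6.2 ends PFS at "the date of first documented disease progression or death from any cause, whichever occurs first". SAP Table 2 dates the uncensored event at the "Date of death or first disease assessment showing PD, whichever occurs first".

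**Scans after progression.** Under Protocol 3.1.2, patients with first progression and no clinical deterioration "may continue study treatment until a repeat scan within 4 to 6 weeks confirms disease progression". SAP 3.1 repeats this. The sentence is not limited to pembrolizumab patients.

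**Minimum time for stable disease.** For stable disease to be the best response, Appendix 3 says "it must also meet the SD criteria at least once after study entry at 6 weeks or longer from baseline". The DCR definition states no minimum.

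**Status of the study.** SAP 4.8 records that Phase 2 was not run and that ORR was made a primary efficacy endpoint for Phase 1b.

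**The concern.** PFS fails a patient at the first documented progression, while the response endpoints keep looking at later scans. One patient can therefore be a PFS failure and also a disease-control or response success. A response first seen after progression would also start a DOR interval after the event that is meant to end it.

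The effect on ORR and DCR goes one way: a best result over a longer set of scans cannot be worse than over a shorter set. It falls on the endpoint that SAP 4.8 promoted for Phase 1b, where results are shown by dosing regimen in very small groups. SAP 3.4.1.1 and 4.5.3 reserve iRECIST for pembrolizumab patients, so a Phase 1b post-progression response has no separate place and falls into the RECIST v1.1 endpoint.

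**Working it through.** The plan gives no figure for this effect and no frequency of scans after progression, so there is nothing of its own to reproduce. The check applies its rules to hypothetical patients.

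**Inputs**
- Visit scoring (Protocol Appendix 3): PD is a sum at least 20% and at least 5 mm above the smallest sum on study, baseline included. PR is at least 30% below baseline. Otherwise SD. Each visit is scored separately, and any new lesion makes the visit PD.
- Scans (Protocol 7.4.1.2): Week 8, then every 6 weeks to Week 26. Repeat scan 4 to 6 weeks after first PD (Protocol 3.1.2).
- Group sizes (Protocol 3.1): cohorts of 3 to 6; 27 to 60 in Phase 1b.

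**1. Timing.** PD at Week 8 puts the repeat scan at 8 + 4 = Week 12 to 8 + 6 = Week 14. That is inside the 26-week ORR window, on treatment for DCR, and past the 6-week minimum for SD. None of these rules blocks the count.

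**2. Scoring.** Take a hypothetical baseline sum of 100 mm and no new lesions.
- Week 8 sum 125 mm: (125 − 100)/100 = +25%, and +25 mm. PD, and a PFS event.
- Repeat sum 115 mm: +15% from the smallest sum (100), below 20%, and no 30% fall. SD.
- Repeat sum 68 mm: (68 − 100)/100 = −32%. PR.

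**3. Resulting endpoints**

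| Sums (mm) | Visits | PFS | Plan read literally | With cut-off at first PD |
|---|---|---|---|---|
| 100, 125, 115 | PD, SD | Event, Week 8 | Best response SD; DCR success | Best response PD; counts in neither rate |
| 100, 125, 68 | PD, PR | Event, Week 8 | Best response PR; ORR and DCR success | Best response PD; counts in neither rate |

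In the second row DOR starts at Weeks 12 to 14. If Table 2's first assessment showing PD is taken as its end, it ends 4 to 6 weeks before it starts. Protocol 9.6.2 also censors responding patients for PFS at their last tumor assessment, so this patient could be read as either an event or censored.

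**4. Who is not affected**
- SD at Week 8, PD at Week 14, SD on the repeat scan: already a DCR success before PD.
- Sums 100, 60, 75, 68: PR (−40%), then PD (+25% and +15 mm from 60), then PR (−32% from baseline, +13% from nadir). Already a responder before PD.
- A new lesion still present on the repeat scan: the visit stays PD.

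So DCR changes only when no qualifying SD, PR or CR came before PD. ORR changes only with no earlier CR or PR and a post-PD response within 26 weeks.

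**5. Size per patient.** Each affected patient adds 1/n:
- cohort: 1/6 = 16.7 to 1/3 = 33.3 percentage points;
- Phase 1b overall: 1/60 = 1.7 to 1/27 = 3.7 points.

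This takes every enrolled patient as being in the Full Analysis Set. Exclusions would make n smaller and the step larger.

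**The case against.** The exposed group is narrow. Routine imaging ends at progression or new therapy (Protocol 7.4.1.2), and other sections have treatment running until progressive disease (synopsis, 3.1, 7.3.3). Treatment past progression is set out in detail only for pembrolizumab patients (3.3, 7.4.1.2), and Phase 2 was not run. This stands as a limit on frequency. It does not remove the general wording of Protocol 3.1.2, which SAP 3.1 repeats. Those passages need to be reconciled with one another.

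SAP 4.5.3 ties the ORR estimates to the first post-baseline assessment, and SAP 4.5.4 applies the same methods to DCR. On one reading, only the first scan counts and post-progression scans drop out. That reading would conflict with the 26-week definition in SAP 3.4.1.1. The wording is too unclear to serve as the missing rule.

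The best-response sentence is in a protocol appendix, and its examples place progression last. They are silent on progression followed by response. That is fair, but the ORR and DCR definitions in the SAP lack a cut-off as well.

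The study is descriptive, and tumor assessments are listed, so such a patient would be visible. This lowers the stakes. It still leaves the choice to be made after the data are seen, which SAP Section 1 says it aims to avoid.

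A reader might also infer that SD could rest on about 3 weeks of drug, since a baseline scan may precede dosing by 21 days (42 − 21 = 21). No routine scan fits this. The first is at Week 8, Day 50, and 7 days early is Day 43, which is 42 days after first dose. Only an unscheduled or early end-of-treatment scan could do it.

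**Conclusion.** The point holds in a limited form. Read literally, the plan credits a first qualifying SD, PR or CR seen only after documented RECIST v1.1 progression, while PFS counts that progression as an event. The error in ORR and DCR can only be upward.

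Its size per affected patient is 1/n: 17 to 33 points in a cohort of 3 to 6, and 1.7 to 3.7 points over 27 to 60 patients. The number of affected patients is not in the documents and is probably small. A reader might infer that DCR is inflated by several points overall, or that every scan after progression inflates it. The documents support neither: any overall figure would only restate an assumed frequency, and patients with a qualifying result before progression are unaffected.

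The conclusion rests on reading Protocol 3.1.2 as covering Phase 1b patients. For ORR, and for DCR if SAP 4.5.4 carries the phrase over, it also rests on not reading SAP 4.5.3 as limited to the first scan. Severity is moderate: the effect touches a primary efficacy endpoint, but in a descriptive study with few patients exposed.

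**What to change.** In SAP 3.4.1.1, 3.4.1.2 and 4.5.3, state that RECIST v1.1 best response, ORR, DCR and the start of DOR use only assessments up to and including the first RECIST v1.1 PD or the start of new anticancer therapy, whichever is first. Say that this overrides the all-time-points wording of Protocol Appendix 3 and the any-time wording of the DCR definition, and record it in SAP 4.8 as a change from the protocol. Show later scans in listings, or under iRECIST for pembrolizumab patients.

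In the same edit:
- reconcile the first-post-baseline-assessment phrase in SAP 4.5.3 with the 26-week ORR definition;
- state that the 6-week minimum for SD in Appendix 3 applies to DCR.

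The cost is SAP wording and one programming condition. No new data are needed. ORR and DCR may come out slightly lower.

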Appendix 4. Immunologic Response Evaluation Criteria in Solid Tumors

(Source: Seymour 2017)

Immunologic Response Evaluation Criteria in Solid Tumors (iRECIST) is based on RECIST v1.1, but adapted to account for the tumor response seen with immunotherapeutic drugs. When feasible, Investigators are encouraged to keep patients on treatment until progression is confirmed by the Investigator, working with local radiology, according to the rules in this section. This allowance to continue treatment beyond the initial radiologic progressive disease (PD) factors in the observation that some patients may have a transient increase in tumor burden after starting immunotherapy and then experience subsequent disease response.

A summary of the adaptations is provided here, with additional detail in the iRECIST publications (Seymour 2017). iRECIST should be used by the Investigator to assess tumor response and progression for the purpose of treatment decisions. These data will be captured in the clinical database.

Assessment at Screening and Prior to RECIST v1.1 Progression

Until radiographic progression based on RECIST v1.1, there is no distinct iRECIST assessment.

Assessment and Decision at RECIST v1.1 Progression

In patients who have an assessment of radiologic PD per RECIST v1.1, the Investigator will decide whether to continue a patient on study treatment until repeat imaging is obtained (using iRECIST to guide treatment decisions). This decision would be based upon the patient's overall clinical condition meeting the criteria for clinical stability defined by the following:

- Absence of symptoms and signs indicating clinically significant progression of disease
- No decline in ECOG performance status
- No requirements for intensified management, including increased analgesia, radiation, or other palliative care
- Absence of rapid progression of disease

Any patient deemed clinically unstable should be discontinued from study treatment and tumor imaging would not be repeated for confirmation of PD by iRECIST.

If the Investigator decides to continue treatment, the patient may continue to receive study treatment, and the tumor assessment should be repeated 4 to 8 weeks later to confirm PD by iRECIST, per investigator assessment.

iRECIST defines new response categories, including immune unconfirmed progressive disease (iUPD;unconfirmed PD) and immune confirmed progressive disease (iCPD;confirmed PD). For the purposes of iRECIST assessment, the first visit showing progression per RECIST v.1.1 criteria will be assigned an overall response of iUPD.

At this visit, the initial target and nontarget lesions identified at baseline will be assessed as usual, with collection of lesion measurements on the target lesion eCRF and tumor states on the nontarget lesion eCRF.

For data collection per iRECIST, the **main difference is in the assessment of new lesions**, which are classified as measurable or nonmeasurable, using the same size criteria as for baseline lesion assessment in RECIST v1.1 (at least 10 mm in long axis [or 15 mm in short axis for nodal lesions]). From measurable new lesions, up to 5 lesions total (up to 2 per organ), may be selected as "new lesions – target." The sum of diameters of these lesions will be calculated but kept distinct from the sum of diameters of target lesions identified at baseline. All other new lesions will be followed qualitatively as "new lesions – nontarget."

Assessment at the Confirmatory Imaging (4-8 Weeks After Assessment of RECIST PD)

Confirmatory imaging should be performed at least 4 weeks, but no longer than 8 weeks following initial iUPD assessment. On the confirmatory imaging, the outcomes of tumor evaluation by iRECIST can be (1) confirmation of progression (with an overall response of iCPD), (2) persistence of unconfirmed progression (with an overall response of iUPD), (3) disease stability (iSD), or (4) response (immune partial response [iPR]/immune complete response [iCR]) as illustrated in Figure 1.

Timepoint of initial **Imaging Results at iRECIST RECIST PD (or subsequent** Confirmatory Response (UPD) Timepoint Discontinue treatment. New lesion (If clinically stable, **iCPD** can continue on study Increase in any existing treatment with sponsor lesions (TL, NTL, new) approval No change in noniUPD rget and new lesions (can have AND Continue treatment rget lesions abov multiple PD threshold IUPD) iUPD No change in non-Continue iSD/ Continue treatment imaging AND iPR threshold* Continue treatment All lesions resolved iCR

Appendix 4, Figure 1: Assessment of Tumor Response Using iRECIST

*PD threshold = +20% & 5 mm increase from nadir

iCPD =immune confirmed progressive disease; iCR = immune complete response; iPR = immune partial response; iSD = immune stable disease; iUPD = immune unconfirmed progressive disease; NTL = nontarget lesion; PD = progressive disease; TL = target lesion

iRECIST Criteria for Confirmation of Progression

Progression is considered as confirmed, with an overall response of iCPD, if ANY of the following occurs:

• Worsening of any of the individual component responses (target lesion, nontarget lesion, or new lesion) that were the basis for the initial overall iUPD determination:

- Target lesions: worsening is a further increase in the sum of diameters of ≥5 mm, compared with any prior iUPD timepoint.
- Nontarget lesions: worsening is any significant growth in lesions overall, compared with a prior iUPD timepoint; this does not have to meet the "unequivocal" standard of RECIST v1.1
- New lesions: worsening is any of the following:
 - O An increase in the measurable new lesion sum of diameters by ≥5 mm from a prior iUPD timepoint.
 - Visible growth of non-measurable new nontarget lesions
 - The appearance of additional new lesions
- Any new factor appears that would have triggered PD by RECIST v1.1

Persistence of iUPD

Progression is considered not confirmed, and the overall response remains iUPD, if the following is observed:

- No worsening of existing tumor burden (target, nontarget, and new lesions) as described above occurs AND
- The target lesion sum of diameters (target lesions identified at baseline) remains above the RECIST-defined threshold for target lesion progression.

The second factor would be applicable only in cases where the target lesion increases at the initial assessment of iUPD met the criteria for progression ($\geq 20\%$ and ≥ 5 mm increase from nadir). Cases where initial iUPD was based upon progression of nontarget lesions or identification of new lesions, but target lesion change does not meet PD criteria would be covered by the section below on Resolution of iUPD.

Additional imaging for confirmation should be scheduled 4 to 8 weeks from the scan on which the iUPD is seen. This may correspond to the next visit in the original visit schedule. The assessment of the subsequent confirmation scan proceeds in an identical manner, with possible outcomes of iCPD, iUPD, and iSD/iPR/iCR.

Resolution of iUPD

Progression is considered not confirmed, and the overall response becomes iSD/iPR/iCR, according to the following:

- No worsening of existing tumor burden (nontarget and new lesion) AND
- The target lesion sum of diameters (target lesions identified at baseline) is not above the RECIST-defined threshold for target lesion progression.

The response is classified as iSD or iPR (depending upon the sum of diameters of the target lesions), or iCR if all lesions resolve. iCR, iPR, and iSD can all be assigned after iUPD has been documented, as long as iCPD was not confirmed. Following a determination of iSD, iPR, or iCR, the next visit that shows radiographic progression, whenever it occurs, is again classified as

iUPD by iRECIST, and the confirmation process is repeated before a response of iCPD can be assigned.

Management Following the Confirmatory Imaging

If repeat imaging does not confirm PD per iRECIST, as assessed by the Investigator, and the patient continues to be clinically stable, then study treatment may continue following the regular imaging schedule. If PD is confirmed, then patients should be discontinued from study treatment.

If an iCPD as defined above, but the patient is achieving a clinically meaningful benefit, and no further increase in the tumor burden is seen at the confirmatory tumor imaging, then an exception to continue study treatment may be considered following consultation with the Sponsor. If study treatment is continued, then tumor imaging should continue to be performed.

Determination of Progression after Assessment of iSD/iPR/iCR

After achieving a response of iSD/iPR/iCR, subsequent iUPD is indicated by any of the following:

- Target lesions
 - Sum of diameters reaches the PD threshold (≥20% and ≥5 mm increase from nadir). The nadir is always the smallest sum of diameters observed throughout the entire study.
- Nontarget lesions
 - If nontarget lesions have never shown unequivocal progression, their doing so for the first-time results in iUPD.
 - If nontarget lesions had shown previous unequivocal progression, and this
 progression has not resolved, iUPD results from any significant further growth of
 nontarget lesions, taken as a whole.
- New lesions
 - New lesions appear for the first time.
 - Additional new lesions appear.
 - Previously identified measurable new lesions show an increase of ≥5 mm in the new lesion sum of diameters, from the nadir value of that sum.
 - Previously identified non-measurable new lesions show any significant growth.

If any of the factors above indicate iUPD, the iUPD evaluation process is repeated, similar to the first occurrence of iUPD. iUPD must be confirmed before iCPD can occur.
